7. INTERVENTIONS

7.1 Name and description of intervention under investigation

Crisis psychoeducation intervention: The plan for the intervention is described here but is subject to change following phase 1 of the study.

Each intervention participant will receive:

- (a) Up to four initial sessions with a “personal mental health worker” (a clinical psychologist or equivalently skilled worker - terminology, desirable qualifications and characteristics to be reviewed in Phase 1). These will focus on: initial relationship building; individualised education about risk factors for relapse; information about accessing and using services and treatments; information on their specific mental health problem; identification of individual risk and protective factors; exploration of individual recovery goals. Meetings may be conducted in person, or via video-conference depending on current Covid-restrictions and participants’ preference. The content of the intervention will be finalised by the coproduction group.
- (b) Production, in electronic or paper form, of a crisis plan/advanced statement, outlining warning signs to monitor strengths and resources, a personalised crisis action plan and details of sources of help and support. This will be adapted to incorporate emerging policy guidance on content of Advance Choice Documents regarding preferences for crisis management.
- (c) Monthly telephone or video call monitoring over one year, initiated by the personal mental health worker, including checking warning signs and prompting coping responses.

The trial intervention will be provided as an addition to mental health care of usual type and quality, received by members of this groups.

Treatment as usual: This will be the routine care that participants receive. This includes multi-disciplinary care from mental health nurses, nursing assistants, psychiatrists, pharmacists, occupational therapists and psychologists in both the inpatient and community setting.

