13.2.4 Recording of Adverse Events

14. All adverse events will be recorded in the medical records in the first instance. All Adverse events will be recorded in the Case Report Form (CRF) following consent.

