14.2 Managing serious adverse events across research sites

Mental health practitioners delivering the trial intervention, their NHS supervisors, and managers of the participating NHS services will be directed to report any adverse events involving trial participants to the relevant site PI without delay. In addition, the study researcher will contact the mental health practitioner's supervisor and involved NHS service manager at each site at least monthly, to ask them to screen service and patient records for AEs for trial participants. A report of the circumstances of the AE, and the informant's view on causation and severity will be sought from the PI or study researcher, who will then contact the study CI without delay. The study CI ([name]), as the trial's Clinical Reviewer and a Consultant Psychiatrist, will complete an SAE form and make final assessments of severity, causality and expectedness, in discussion with the PI where possible. The CI will then send the completed SAE form to the Sponsor and the site PI, and disseminate any necessary safety information to the other site PI.

SAEs will be followed up and screened for each participant until the participant's 6-month follow-up research interview and active involvement in the study are completed.

SAEs will be reported to the sponsor until the end of the trial. Follow-up SAE forms (clearly marked as follow-up) will be completed and emailed to the JRO if required as further information becomes available.

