24.1 APPENDICE 1: Schedule of Assessments

	Screening (Pre-treatment assessment)	Intervention phase	6-month post baseline (post- therapy)	12-month post baseline (follow- up)	24-month post baseline (follow-up)
	Day 1 to Day -7	Week 1 - 52	Week 24	Week 52	Week 104
Informed Consent	X				
Eligibility confirmation	X				
Randomisation	x				
Compulsory admission				X	X
CSQ	x		x	X	
QPR	X		X	X	
REQOL	X		X	X	
MHCS	X		X	X	
TA	X		X	X	
SE	X		X	X	
CSRI	X		X	X	
Intervention delivery		X			
Qualitative interview (intervention arm participants only)			X*		

CSQ- Client satisfaction Questionnaire; CSRI – Client Service Receipt Inventory; MHCS – Mental Health Confidence Scale; QPR – Process of Recovery Questionnaire; REQOL – Recovering Quality of Life; SE – Service Engagement; TA – Therapeutic Alliance; *will be conducted 6=9 months post randomisation

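### Month 6 is the only dated end of SAE screening, although the intervention runs for a year, and the second end condition is undefined

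*Protocol*

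**What the plan says.** **End of screening.** Section 14.2 states: "SAEs will be followed up and screened for each participant until the participant's 6-month follow-up research interview". The sentence does not stop there. Its full end condition is "6-month follow-up research interview and active involvement in the study are completed". The second part carries no date and no definition.

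**Other safety provisions.** In the same section, the study researcher contacts the practitioner's supervisor and the service manager "at least monthly, to ask them to screen service and patient records for AEs for trial participants". Practitioners, their supervisors and service managers "will be directed to report any adverse events involving trial participants to the relevant site PI without delay". Neither duty has an end date of its own. The section adds that "SAEs will be reported to the sponsor until the end of the trial". Section 13.2.4 says "All Adverse events will be recorded in the Case Report Form (CRF) following consent", again without an end date.

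**Length of the intervention.** Section 7.1 lists "Monthly telephone or video call monitoring over one year, initiated by the personal mental health worker". Section 8.3.1 places this year of calls after up to four initial sessions. Appendix 1 shows the intervention phase as weeks 1 to 52 and the 6-month visit at week 24, under the heading "6-month post baseline (post- therapy". Appendix 1 has no row for adverse events.

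**Later follow-up.** Section 8.4.3 repeats the secondary measures at 6 and 12 months and takes service use from records at 12 and 24 months.

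**The concern.** Month 6 is neither the end of the intervention nor the last research interview, so it is an odd point at which to end safety surveillance. The post-therapy label in Appendix 1 makes it look as though month 6 was taken to be the end of therapy.

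Two things are at stake. First, active screening might lapse while participants are still receiving the intervention. Later SAEs would then reach the team less systematically. Second, if sites take active involvement to mean contact with the intervention worker, the two arms would be screened for different lengths of time, and a comparison of SAE counts between arms would be biased by design. A pilot meant to inform a definitive trial should not leave that open.

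**Working it through.** The protocol gives no figure of its own to reproduce. The check compares the stated time windows.

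**Inputs**
- End of scheduled intervention: week 52 (Appendix 1).
- 6-month visit: week 24 (Appendix 1).
- Arm sizes: 40 and 40 (sections 3.2.2 and 11.2).
- Assumption: all 80 participants are recruited and remain under follow-up, so the participant-time figures are maxima.

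**Time outside screening if it stops at the 6-month interview**
- Weeks: 52 − 24 = 28. Share of the scheduled intervention: 28 / 52 = 54%.
- Intervention arm: 40 × 28 = 1,120 participant-weeks; 1,120 / 52 = about 21.5 participant-years.
- Both arms: 80 × 28 = 2,240 participant-weeks; 2,240 / 52 = about 43 participant-years.
- Cross-check in calendar months: 12 − 6 = 6 months, or 50%; 40 × 0.5 = 20 participant-years in the intervention arm and 80 × 0.5 = 40 over both arms. The small gap arises because Appendix 1 puts month 6 at week 24.

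**What the undefined condition does to the window**

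| Meaning given to active involvement | Intervention arm screened to | Control arm screened to | Consequence |
|---|---|---|---|
| Ends at about the 6-month interview | week 24 | week 24 | 28 of 52 intervention weeks not actively screened |
| Contact with the intervention | about week 52 | week 24 | arms differ by about 28 weeks |
| Research interviews, including month 12 | about week 52 | about week 52 | about 0 weeks lost, arms equal |

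Only the third reading is free of trouble, and the protocol does not state it. It also makes the mention of the 6-month interview redundant: if involvement always lasts to month 12, the 6-month condition can never decide when screening ends.

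One further mismatch bears on the fix. If the year of calls follows the initial sessions (section 8.3.1), the last call can fall after month 12, whereas Appendix 1 closes the intervention phase at week 52.

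**The case against.** The best defence is the wording itself. The sentence requires two things to be completed, and active involvement can plausibly include the year of calls and the 12-month interview. Read that way, screening covers the whole intervention. This stands as a possible reading, and it rules out some stronger inferences that a reader might draw.

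- *Harms in the second half of the intervention are not screened for.* The text does not establish this. It leaves it open.
- *After month 6 only volunteered events are captured, mainly from workers who see one arm.* Not supported. Service managers must also report, and their duty covers trial participants generally. The monthly record check has no separate end date, and CRF recording has no 6-month limit. Readmissions in both arms are taken from records at 12 and 24 months (section 8.4.2), although that extraction is not a screen for other kinds of SAE.
- *Reporting to the end of the trial contradicts earlier screening.* It does not. A duty to report SAEs that become known can outlast active screening.
- *Nobody would notice, because no data monitoring committee is planned.* The Trial Management Group meets monthly and reviews SAEs (section 15.1). The independent steering committee reviews SAEs thought to be linked to the trial and other safety concerns (section 15.2). Both, however, depend on what is captured.

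It can also be said that no adverse events are expected from the intervention (section 13.2.3) and that no feasibility or primary outcome turns on this sentence. Both are true, and they limit the weight of the point. They do not settle when screening ends or whether it ends at the same time in both arms.

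**Conclusion.** The point holds as an unclear and poorly fitting endpoint, not as a proven gap. The only dated end of SAE screening is month 6. It does not match a one-year intervention and a 12-month interview, and the condition that might extend it is undefined. A site following the text could reasonably stop at month 6 or screen the arms for unequal periods.

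The size depends on the reading: from about 0 to 28 of 52 scheduled intervention weeks, that is up to about 21.5 participant-years in the intervention arm and about 43 over both arms. These maxima assume full recruitment, no loss to follow-up and the week numbers in Appendix 1. The time concerned would have less systematic capture, not no capture. An imbalance between arms is a risk under one reading; the protocol does not prescribe it.

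**What to change.** Reconcile sections 7.1, 8.3.1, 8.4.3, 14.2 and Appendix 1. In section 14.2, replace the 6-month endpoint and the undefined involvement condition with one fixed time from randomisation. That time should be identical in both arms, no earlier than the 12-month follow-up, and late enough to cover the scheduled monitoring calls, with the same at-least-monthly record screening throughout.

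A rule tied to each participant's last monitoring call would not do: controls have no such calls, so the intervention arm could again be screened for longer.

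In Appendix 1, remove or correct the post-therapy label on the 6-month column.

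The cost is a small amendment and about six or more further months of a record check already in place. It should be settled before participants pass month 6, because prospective screening cannot be fully recreated afterwards.

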14.3 Unblinding

The CI/PI will document any unblinding and the reasons for it on the CRF and unblinding log and will file this, in the site file. It will also be documented at the end of the trial in any final trial report and/or statistical report.

The CI/Investigating team will notify the JRO in writing as soon as possible following the code break detailing the necessity of the code break.

In the absence of a Data Safety Monitoring Committee, the written information will be disseminated to the chair of the Trial Steering Committee for review in accordance with the DSMC Charter.

14.4 Reporting Urgent Safety Measures

If any urgent safety measures are taken the CI/ PI shall immediately and in any event no later than 3 days from the date the measures are taken, give written notice in the form of a substantial amendment to the relevant REC and Sponsor of the measures taken and the circumstances giving rise to those measures.

14.5 Protocol Deviations and Violations

A reportable protocol violation is a breach which is likely to effect to a significant degree:

- (a) the safety or physical or mental integrity of the participants of the trial; or
- (b) the scientific value of the trial.

The Sponsor will be notified immediately of any protocol violations during the trial conduct phase by completion of the online JRO Research Incident Reporting Form:

<https://redcap.slms.ucl.ac.uk/surveys/?s=NE5dypTdFo>. All protocol violations must be recorded on the Protocol Violation Log and filed in the site file.

14.6 NHS Serious Incidents and Near Misses (if applicable)

A serious incident or near miss is any unintended or unexpected event that could have or did lead to harm, loss or damage that contains one or more of the following components:

- a. It is an accident or other incident which results in injury or ill health.
- b. It is contrary to specified or expected standard of patient care or service.
- c. It places patients, staff members, visitors, contractors or members of the public at unnecessary risk.
- d. It puts the Trust in an adverse position with potential loss of reputation.
- e. It puts Trust property or assets in an adverse position or at risk.

Serious Incidents and near misses will be reported to the Sponsor and Trust Quality & Safety department as soon as the study team becomes aware of them.

14.7 Complaints from research participants

In the first instance, research participant complaints (patients or health volunteers) will be reported to the CI/PI to investigate, as documented in the patient information sheet(s), and to the Sponsor via [contact], following the *UCL Complaints from Research Subjects about UCL Sponsored Studies and Trials* policy. For participants who are NHS patients, complaints will be reported to the NHS Complaints Manager at the Trust where the recruitment and study procedures were undertaken. Complaints from NHS patients are handled under NHS complaints policies and procedures, with involvement from PALS and the Sponsor where necessary.

15. OVERSIGHT COMMITTEES

15.1 Trial Management Group (TMG)

The TMG will include the Chief Investigator, Co-CI, study co-applicants, and trial staff. The TMG will be responsible for overseeing the trial. The group will meet monthly and will send updates to PIs.

The TMG will review recruitment figures, SAEs and substantial amendments to the protocol prior to submission to the REC. All PIs will be kept informed of substantial amendments through their nominated responsible individuals.

15.2 Other committees

A Trial steering Committee of independent researchers, including: a service user-researcher, a clinical academic, a social scientist and a statistician, will be set up and meet at least six monthly during the course of the study to provide independent oversight and advice. The steering committee will advise on development of the study intervention and trial procedures. The committee will also review serious adverse events thought to be linked to the trial or other concerns regarding the safety of the trial.

A Data Monitoring Committee is not planned for this pilot trial, which is not collecting interim data and has no pre-planned stopping criteria. The study management team will ask the steering committee to review this plan before the start of the trial in the second year of the study and will recruit a DMC if the TSC advises this.

16. REGULATORY REVIEW AND PATIENT AND PUBLIC INVOLVEMENT

16.1 Regulatory Review

The Sponsor will ensure that the trial protocol, participant information sheet, consent form, GP letter and submitted supporting documents have been approved by the appropriate research ethics committee, prior to any participant recruitment. The protocol, all other supporting documents including and agreed amendments, will be documented and submitted for ethical and regulatory approval as required. Amendments will not be implemented prior to receipt of the required approval(s).

The study was deemed to require regulatory approval from the following bodies (NHS REC Favourable Opinion and HRA Approval). **Before any site can enrol patients into the study**, the Chief Investigator/Principal Investigator or designee will ensure that the appropriate regulatory approvals have been issued, and NHS Confirmations of Capacity and Capability and Sponsor green lights are in place.

For any amendments to the study, the Chief Investigator or designee, in agreement with the Sponsor, will submit information to the appropriate body in order for them to issue approval for the amendment. The Chief Investigator or designee will work with sites (R&D departments as well as the study delivery team) to confirm ongoing Capacity and Capability for the study.

All correspondence with the Sponsor, REC and HRA will be retained. The Chief Investigator will notify the Sponsor and REC of the end of the study.

It is the Chief Investigator's responsibility to produce the annual progress reports when required; an annual progress report (APR) will be submitted to the Sponsor and REC within 30 days of the anniversary date on which the favourable opinion was issued, and annually until the study is declared ended.

Within 90 days after the end of the trial, the CI will ensure that the main REC is notified that the trial has finished. If the trial is terminated prematurely, those reports will be made within 15 days after the end of the trial.

Within one year after the end of the study, the Chief Investigator will submit a final report with the results, including any publications/abstracts, to the Sponsor and to the REC and HRA.

16.2 Peer Review

The study has been peer reviewed in accordance with the requirements outlined by UCL. The Sponsor considers the procedure for obtaining funding from the National Institute of Health Research to be of sufficient rigour and independence to be considered an adequate peer review.

16.3 Patient and public involvement (PPI)

The PPI lead will be [name]. He will work with BLE and the study post-doc researcher to set up, organise and support the Co-production Group. We include funding for him to have access to a mentor who is an experienced lived experience researcher monthly during the first six months of the study and quarterly thereafter.

The Co-Production group will include around eight people with relevant lived experience, most as service users and at least two as carers. PN will be included along with 2 or 3 other members of the MHPRU to provide continuity with previous work: a further 4 or 5 will be recruited through advertisement. The Co-Production group will meet monthly through the initial eight months of the study to take the key decisions regarding intervention adaptation. This will include reviewing and iteratively refining study materials, including recruitment materials, psychoeducation materials and study manuals.

We also include funding for members of the Co-Production group to conduct the qualitative interviews with service users during the development phase of the project. In preparation, they will receive training sessions based on training already developed and delivered within the PRU and the UKRI Loneliness and Social Isolation in Mental Health Network, in qualitative interviewing skills and in how to participate in qualitative data analysis. We have costed for an expert in qualitative methods training at UCL to deliver this.

In Phase 2, the Co-Production Group will meet less frequently, but will continue to monitor and advise on study recruitment and retention, and to advise on any dilemmas or difficulties encountered. Members of the Co-Production Group with relevant lived experience will again conduct the qualitative interviews during this phase, and finally will review the intervention to recommend any adaptations or refinements prior to a full trial.

17. MONITORING AND AUDITING

A trial specific oversight and monitoring plan will be established for studies. The trial will be monitored in accordance with the agreed plan. The degree of monitoring will be proportionate to the risks associated with the trial. Risk will be assessed on an ongoing basis by the Chief Investigator, and adjustments made accordingly (in conjunction with the Sponsor).

The Chief Investigator will be responsible for the day to day monitoring and management of the study. The Chief Investigator will ensure there are adequate quality and number of monitoring activities conducted by the study team. This will include adherence to the protocol, procedures for consenting and ensure adequate data quality.

The Chief Investigator will inform the Sponsor should he/she have concerns which have arisen from monitoring activities, and/or if there are problems with oversight/monitoring procedures.

The UCLH/UCL Joint Research Office, on behalf of UCL as Sponsor, will conduct random audits on a selection of studies in its clinical research portfolio. Monitoring and auditing will be conducted in accordance with the UK Policy Framework for Health and Social Care Research, and in accordance with the Sponsor's monitoring and audit policies and procedures.

18. TRAINING

The Chief Investigator will review and provide assurances of the training and experience of all staff working on this study. Appropriate training records will be maintained in the study files.

19. INSURANCE AND INDEMNITY

University College London holds insurance against claims from participants for harm caused by their participation in this clinical study. Participants may be able to claim compensation if they can prove that UCL has been negligent. However, as this clinical study is being carried out in a hospital, the

hospital continues to have a duty of care to the participant of the clinical study. University College London does not accept liability for any breach in the hospital's duty of care, or any negligence on the part of hospital employees. This applies whether the hospital is an NHS Trust or otherwise.

Participants may also be able to claim compensation for injury caused by participation in this clinical study without the need to prove negligence on the part of University College London or another party. Participants who sustain injury and wish to make a claim for compensation should be advised to do so in writing in the first instance to the Chief Investigator, who will pass the claim to the Sponsor's Insurers, via the Sponsor's office.

Hospitals selected to participate in this clinical study shall provide clinical negligence insurance cover for harm caused by their employees and a copy of the relevant insurance policy or summary shall be provided to University College London upon request.

Additionally, UCL does not accept liability for sites such as GP surgeries in primary care; investigators/collaborators based in these types of sites must ensure that their activity on the study is covered under their own professional indemnity.

